**Background and Rationale:**

Individuals with bipolar disorder (BD) are prone to chronic medical conditions leading to mortality rates two to three times that of the general population and cardiovascular (CV) disease accounts for more than two-thirds of these deaths (Osby, Brandt, Correia, Ekblom, & Sparen, 2001; Ramsey et al., 2013). While there are multiple factors contributing to the profound morbidity and premature mortality in people with BD, there is an immediate and correctable course of action to reduce CV risk in this population. Poor adherence to antihypertensives, estimated to occur in 50-80% of patients (Costa, 1996; Cramer, Benedict, Muszbek, Keskinaslan, & Khan, 2008), significantly increases the risk of acute CV events but is a modifiable factor that when treated, can make a profound positive impact on health outcomes. Given the dramatic decrease in CV events since the introduction of antihypertensives in the general populace (Corrao et al., 2011), it is reasonable to expect that similar gains could be achieved by optimizing adherence to antihypertensives in persons with BD.

Current reviews indicate insufficient evidence for effective interventions that improve adherence to antihypertensives (Nieuwlaat et al., 2014; Viswanathan et al., 2012). Similarly, while there is ample literature documenting the enormity and negative effects of psychotropic medication non-adherence in BD (Hong, Reed, Novick, Haro, & Aguado, 2011), there are a lack of effective interventions to enhance psychotropic medication adherence and improve clinical outcomes (Nieuwlaat et al., 2014). Given that addressing adherence to both psychotropic and non-psychotropic medications simultaneously is likely to be both more effective and sustainable, we propose developing a practical intervention which addresses both types of medication adherence.

The Attitude-Social Influence-Efficacy (ASE) model (De Vries & Mudde, 1998) frames adherence to medication as deriving from attitudes (A), social influence (S), and self-efficacy (E). However, adherence also requires intact prospective memory, the ability to remember to do a behavior in the future, which tends to be impaired in those with BD (Bogner, de Vries, O'Donnell, & Morales, 2013; Lee et al., 2010; Zogg, Woods, Saucedo, Wiebe, & Simoni, 2012). Given this deficit, even when an individual has the intention to take medication, they lack the planning or organizational abilities to do so consistently (Zogg et al., 2012). Thus, in order to change and sustain medication adherence in this and similar populations, one must address both ASE and prospective memory. This m-Health intervention primes habit formation by targeting behavioral intention using customized psychoeducational and motivational texts with social reference followed by contextual cues, reminders, and immediate positive reinforcement, to create a strong and automatic habit of taking medication which will be sustainable despite variability over time in behavioral intent.

[figure not shown]

Figure 1: Diagram of expanded ASE model

This study aims to test the feasibility, acceptability and effectiveness of a customized m-Health texting intervention built on the Individualized Texting for Adherence Building (iTAB) platform on antihypertensive adherence and systolic blood pressure in hypertensive persons with BD. This practical, customized intervention, intended to improve adherence to antihypertensives and BD medication among high risk individuals, will be suitable for implementation in either primary care or mental health settings and may reverse the unacceptably high morbidity and mortality in this population.

This study has one specific aim:

**Specific Aim 1:** To test the acceptability, feasibility and effectiveness of iTAB-CV to improve adherence to antihypertensives based on self-reported Tablets Routine Questionnaire (TRQ) and a medication event monitoring system (eCAP).

**Hypothesis 1:** iTAB-CV will improve adherence to antihypertensives in non-adherent persons with BD and HTN.

**Hypothesis 2:** Participants will respond to at least 75% of text messages.

**Hypothesis 3:** At least 75% of participants will find iTAB-CV acceptable based on exit interviews.

**Exploratory Aims:** *Secondary outcomes* Change in systolic BP, change in TRQ for BD medications, change in attitudes and self-efficacy for adherence, health status, healthcare utilization (number of hospitalizations and ER admissions), and psychiatric symptoms. Habit strength, prospective memory and mood will be evaluated as possible variables of interest.

**Methods:**

**Overview:**

This study will test an adherence intervention (iTAB-CV) delivered via interactive text messaging which first targets behavioral intent and then adds cues/reminders and reinforcement to form the habit of taking antihypertensives in non-adherent individuals with BD. Thirty eight individuals with BD and HTN being treated with evidence-based antihypertensive agents and mood stabilizing or antipsychotic medications who are non-adherent with their HTN medicine will be enrolled. This phase uses a prospective cohort design with participants serving as their own control. We will test the iTAB-CV intervention quantitatively for feasibility and acceptability as well as for efficacy in increasing adherence to antihypertensives, decreasing systolic blood pressure, and increasing adherence to BD medication.

[figure not shown]

Figure 2: Diagram of Phase II Design

All study participants will be followed for a 3-month period. iTAB-CV, delivered via mobile phone, is intended to be a brief adjunct to standard primary care and mental health treatment. All individuals will continue to receive

treatment as usual with their regular provider(s). Individuals who meet eligibility criteria will have a 30 day run-in period in which their medication adherence will be measured with TRQ and MEMS but without an additional intervention. Following the run-in period, Stage 1 of the iTAB-CV intervention will be introduced. A member of the study team will conduct an interview in order to customize iTAB-CV for each participant at the baseline session. In the first month of iTAB-CV, participants will receive alternating daily texts with psychoeducational and motivational content once daily and a daily mood rating request to both monitor their mood and to determine engagement with the iTAB-CV intervention. In the second stage of iTAB-CV, participants will receive daily texts which will include medication reminders, contextual cues, and immediate reinforcement for medication taking behavior in addition to the content from stage 1. Assessments that include evaluation of treatment adherence, psychiatric symptoms, self-efficacy for medication taking behavior, illness beliefs, medication attitudes, and habit strength for both antihypertensive and BD medications will be conducted at four time points over a 3-month time period (screening, baseline/week 4, week 8, and week 12). Blood pressure will be measured at each of the four contacts. Individuals who drop out of the intervention, and who agree, will be followed up with outcomes assessments over the same 3-month time period that they would have been evaluated had they remained in the study.

## **Participants:**

### **Inclusion criteria:**

1. Participants will have a clinical diagnosis of BD for at least 2 years as determined by a standardized diagnostic interview, the Mini-International Neuropsychiatric Interview (MINI) (52)
2. Have stage 1 or 2 HTN with a systolic pressure  $\geq 130$
3. Carry a diagnosis of HTN per patient self-report  $\geq 6$  months prior to enrollment
4. Have been prescribed at least one regularly scheduled antihypertensive medication for  $\geq 3$  months since diagnosis
5. Have self-reported poor adherence to at least one antihypertensive medication defined as missing 20% or more of medication within either the past week or past month (53-56) as identified by the Tablets Routine Questionnaire (TRQ)
6. Be able to participate in psychiatric interviews

### **Exclusion criteria:**

1. Unable or unwilling to participate in psychiatric interviews. This will include individuals, who may be too psychotic to participate in interviews/rating scales
2. Unable or unwilling to give written informed consent to study participation
3. Under the age of 21
4. In the interest of patient safety, individuals who are at high immediate risk for suicide will be excluded from study participation. The suicide risk assessment will be informed by standardized assessments of psychiatric symptoms and the Mini-International Neuropsychiatric Interview (MINI). In the event that a potential study participant is determined to be at high risk for suicide, that individual will not be enrolled and the study staff will immediately implement procedures for the safety of the individual. Once such individuals are deemed stable, they may be once again considered for inclusion in the research.
5. Individuals who are monolingual, non-English speaking will be excluded. Given the relatively small sample size in this study, it would not be practical to conduct sub-group analyses. Also, the study assessment tools are not available in other languages and would be impractical to develop. Based upon our BD adherence work, which drew upon a populations similar to this trial, there were no potential subjects who were excluded from the studies due to inability to speak English.
6. Illiterate participants will be excluded because reading is an essential skill required to complete self-report questionnaires administered during the study as well as to utilize the text messaging intervention.
7. Unwillingness to receive text messages

The study will not exclude individuals based on physical health status, although some individuals may choose not to participate because of their own health status. Inclusion criteria for study participation are purposely quite broad in order to represent a “real-world” BD population that typically receives care in clinical settings.

## **Vulnerable Populations:**

### *Pregnant Women:*

According to 45 CFR 46.204, pregnant women may be involved in this research study because the study risks to the pregnant woman and fetus are not greater than minimal risk, and the purpose of the research involves testing a psycho-educational intervention to improve psychiatric treatment adherence which is important for achieving the objectives of the research. Each individual providing consent will be informed of reasonable foreseeable impact of the research on the fetus. There will be no inducement, monetary or otherwise offered to terminate a pregnancy, and individuals engaged in the research study will have no part in determining the viability of a neonate.

If a woman becomes pregnant while in the study, she may choose to continue or discontinue participation. Partners of pregnant subjects or pregnant partners of subjects will not participate in this research.

### *Employees of UHHS and Case:*

Employees of UHHS and Case may be included in the study provided the following:

- they are not direct reports to the Department of Psychiatry at UHHS, or the Department of Psychiatry, Department of Neurology, or the Center for Health Care Research and Policy at Case Western Reserve University
- they are not employees of the principal investigator or co-investigators, with direct involvement in the proposed study or other studies under the principal investigator or co-investigators

The informed consent documents contain the standard language informing any potential participant that is an employee that they are not being recruited specifically because of their employee status and that their choice to withdraw from the study does not in any way affect their status as an employee.

### *Major Psychiatric Illness:*

Inclusion of participants with bipolar disorder is necessary, because the main purpose of the study is to find an effective psycho-educational intervention to improve psychiatric treatment adherence in those with bipolar disorder. Those with other major psychiatric illnesses will not be included because this study is specific to only those with bipolar disorder.

Given that the incidence of comorbid psychiatric conditions is high in patients with bipolar disorder, they will not be excluded for having additional psychiatric diagnoses.

## **Relevant Excluded Populations**

### *Non-English Speaking Participants:*

Non-English speaking individuals will be excluded, because study assessment tools are not available in other languages and would be impractical to develop.

### *Illiterate Participants:*

Because reading is an essential skill required to complete self-report questionnaires administered and read text messages during the study, illiterate individuals will be excluded from the study.

## **Recruitment:**

Patients will be recruited by a variety of methods:

- the Principal Investigator's clinical practice
- the Co-Investigators' clinical practices
- Family Practice and Department of Internal Medicine, University Hospitals Cleveland Medical Center
- the inpatient psychiatric unit at the UH Richmond Medical Center:  
[name]  
[name]
- referrals from other mental health providers
- responses from community outreach to different Community Mental Health Centers (CMHC), and other organizations that serve this population
- IRB-approved study flyers

Psychiatrists, primary care physicians, and other clinicians will be asked to discuss this project with eligible individuals. CMHC and other organizations that serve this population will be asked to coordinate introductions of study staff to discuss this project with eligible individuals. Individuals referred with BD will be considered for possible inclusion in the study. A Screening Form for each patient will be completed regardless of whether the patient is ultimately enrolled. The form will detail reasons for exclusion, allowing an estimate of sample generalizability in relation to the wider population of people with BD.

Patients recruited in response to an IRB-approved recruitment method may be prescreened under the IRB-approved protocol, "Prescreening and Recruitment for the Mental Health Effectiveness Research Program and Neurological and Behavioral Outcomes Center" (MHERP/NBOC Prescreen) [IRB # 03-10-09].

### **Study Personnel:**

The study PI will oversee and be responsible for all aspects of the study including study regulatory matters, human subjects requirements, study implementation, study staff supervision, and data collection, analysis and reporting.

### **Specific Procedures:**

In phase 2, all eligible participants will receive iTAB-CV. After providing informed consent, all participants will undergo screening followed by a 30-day run-in period in which adherence will be measured using eCAP and self-report. During the 30-day run-in period, participants will continue to receive care as usual and serve as their own control with no intervention. Participants will be provided with the eCAP device for the antihypertensive agent that is missed most often. In the case of more than one such agent, the antihypertensive dosed most often. If there is again more than one such agent, the most recently prescribed agent will be chosen. Based on our experience with MEMs, the Hawthorne effect wears off after 1-2 weeks. After the 30-day run-in period, participants will receive 30 days of stage one of iTAB-CV. The study PI or study staff will conduct an interview in order to customize iTAB-CV for each participant at the baseline session.

In stage one of iTAB-CV, participants begin receiving 1 daily educational/motivational customized text messages addressing medication attitudes, social influences, and self-efficacy which will alternate between antihypertensives and BD medications without reminders and 1 daily mood rating. Participants will identify any stems that they don't want to receive and can write in their own personalized messages. At the 8 week meeting, the study PI or study staff will conduct a brief 2nd iTAB-CV interview to determine the types of medications taken (antihypertensives and/or bipolar medications) and at which times of day as well as to pick reminders/reinforcement texts that the participant wants to receive for stage two.

Stage two of iTAB-CV includes the addition of customized context cues/reminders and immediate reinforcement for medication taking behavior in addition to 1 daily motivational mood rating. The number of texts per day will be determined based on the number of times a day that medications are prescribed (up to four a day). Assessments that include evaluation of treatment adherence, psychiatric symptoms, health status, self-efficacy for medication taking behavior, illness beliefs, medication attitudes, and habit strength for both antihypertensive and BD medications will be conducted at four time points over a 3-month time period (screening, baseline/week 4, week 8, and week 12). Blood pressure and weight will be measured at each of the four contacts. Height will be measured at screen. Individuals who drop out of the intervention, and who agree, will be followed up with outcomes assessments over the same 3-month time period that they would have been evaluated had they remained in the study. Table 1 outlines the study schedule of events/assessments.

Individuals will receive reminder telephone calls or text messages during the 2 weeks prior to their scheduled appointment. Individuals will be requested to provide three additional contacts who may assist in facilitating contact with the participant should the individual miss follow-up appointments and if difficulty arises in contacting the individual to re-schedule follow-up (for example, change of address or telephone number). In order to optimize study retention, study staff will maintain personal contacts with study participants via greeting/post cards for birthdays and holidays and regular contact for "location checks" between assessment periods.

One month post study completion, the PI or research study staff will call the individual and will administer the TRQ over the phone for bipolar and blood pressure medications.

## **Intervention:**

### **iTAB-CV Theoretical Basis, Content, Format**

Individuals with BD tend to have erratic lifestyles, and the present intervention is not dependent on frequent contact between provider and patient. People with BD have difficulty with adherence and rates of attendance at clinic-based sessions are poor. This intervention circumvents this problem by administering the intervention on a mobile phone.

In iTAB-CV, sending texts is automated. The iTAB-CV intervention is highly scalable within and across patient populations. The majority of effort in a texting intervention is in the initial programming of the automated system. Once the script is in place, the intervention can be extended for longer periods of time, modified to increase the pool of queries and reminders, altered to include additional medications. iTAB-CV is personalized with texts that are specific to the person, medication and timing. Moreover, iTAB-CV uses the participant's own words for both reminders and reinforcers. iTAB-CV asks the participant to respond to reminders and queries so the intervention is interactive unlike an alarm clock or other programmed devices. iTAB-CV is flexible and can send reminders consistent with the participant's schedule. If medications are switched during the study, we can update iTAB-CV. Also, iTAB-CV will randomly select from a possible pool of reminders and reinforcers, assuring that texts do not become stale. The texts will be customized to overcome existing barriers to adherence.

### **iTAB-CV:**

At the initial visit we will gather the following information to personalize electronic reminders about medications according to the following steps:

- 1) Identify medications: At the initial assessment we will identify the type of medications taken by each participant at what time of day (participants will be asked to bring all medications to their initial appointment) for hypertension and bipolar disorder. For tracking and reminders, we will identify regularly prescribed medicines for hypertension and bipolar disorder.
- 2) Create categorical description of medications: We will not refer to a specific medication name but rather a medication category (antihypertensive versus bipolar medication) ask participants what name they would like to use to describe this category. We considered using a code name for all participants but those in the 3 patient focus groups indicated that they preferred to use the actual disorder names. Given that it is possible that particular participants may find the name of the disorder stigmatizing, they will have the option to pick their own title to refer to the disorder such as unrelated initials.
- 3) Create personalized reminders: Participants will create their own personalized reminders and remove stems that they don't like. For example, persons may choose to say: "Remember to take ...", or "Your health is important, take..." We will provide a menu of reminder options for participants and they will mark those that they don't want to receive. In order to decrease the tendency to ignore a consistent reminder, the program will be automated to randomly choose and deliver one of the reminder stems created by the participant.
- 4) Identify ideal time for reminders: We will work with participants to identify the best time to send the reminders in order to comply with prescription recommendations. Reminders will be customized for each medication or group of medications. We will also make note of times that participants don't want to receive texts (before or after a certain time of day).
- 5) Confirm receipt of message: Participants will be asked to confirm receipt of their message.

A final personalized example of the reminder might be: "Your health is important, remember to take your HTN medication. Please reply 1 to confirm receipt of this message."

We will also send text messages once a week that reinforce good adherence to responding to text messages to keep participants engaged (e.g., "Great job responding to all the messages this week!") (See Appendix #3

for sample texts). If they did not respond, they will be encouraged to do so moving forward (e.g. “We really want to hear from you; we hope you will respond to your messages next week!”).

**Electronic Reminder Device:** We will provide participants with mobile devices and we will purchase bulk ‘minutes’ in order to provide the text message intervention. Importantly, participants will not be responsible should they lose or break the device. Participants may use the device for other purposes (e.g., phone calls, calendar functions) as they wish. Participants along with research staff will collaboratively identify a time during the day in which the reminders will occur. Once enrolled in the study, participants will receive full compensation even if they miss all reminders.

**Psychoeducation and training to use electronic device:** All participants will receive a standardized brief psychoeducational presentation with information about hypertension and bipolar disorder as well as training on how to use the electronic device at the 4 week visit.

Participants will respond to a daily mood rating text once a day at the end of the day. Indication of severe low or high moods will trigger an automated text that will direct the participant to go to the ER in case of emergency. After 3 such texts, the system will automatically notify study staff who will follow up with the participant with a phone call.

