**Risks associated with study participation:**

This study involves completing a set of self-report instruments, along with rating interviews and an intervention customization interview. All of these instruments have been utilized in outpatient research settings and are not associated with risks to patients. The iTAB-CV intervention to enhance treatment adherence involves the use of cognitive and behavioral strategies including psychoeducation, motivational interviewing, context cues/reminders, and positive reinforcement all delivered via text messaging.

The risks to the subjects will be primarily those of talking about some matters, which they may find uncomfortable. Participants do not have to answer upsetting questions, and may discontinue the interview if they wish. It is also possible that the intervention will have no effect on treatment adherence and that receiving texts may become an annoyance. Participants have the option of not responding to texts. They can also stipulate times of the day during which they don't want to receive texts.

Furthermore, the text messages will query regarding daily mood ratings. These approaches are not generally known to increase risk to individuals. Individuals with bipolar disorder are already at risk for depression and possible suicidality. While this intervention is unlikely to increase these risks, it may be able to detect them more readily given the daily mood ratings. There is an automated texting sequence to address texts indicating severely low or high mood which will provide the participant with information on how to access immediate emergency services. If there are 3 such mood ratings in a row, an automatic text will be sent to the research assistant who will follow up by phone with the participant.

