**Data security:**

Research files are not available to any unauthorized person. Research data are collected and stored using UH REDCap. Any paper assessment forms are stored in file cabinets in the locked research offices of the PI on the 7th floor of the W.O. Walker Center at [name]. The list that links study ID codes with subject names and all forms bearing subject names will be stored in a password protected file in a folder only accessible to research team personnel on the secure UH server and/or REDCap. Data analysis files will also be stored in the secure folder on the UH network.

Data Safety and Monitoring will be the responsibility of 1) The study's principal investigator ([name]), 2) The local Institutional Review Board (IRB), and 3) a DSMB.

With regard to loss of confidentiality associated with the mobile device, no personally identifying information will be texted by the study team or stored on the device unless the participant chooses to do so. Therefore, if a device is misplaced, there is minimal likelihood that any loss of confidential information will occur.

Adverse events will be assessed and recorded at every visit following the Screening visit. Assessments will include observations by investigators, spontaneous reporting by subjects, and standard non-leading questions. For every adverse event, the PI will provide an assessment of the severity, duration and causal relationship to study intervention, and document all actions taken with regard to study intervention, as well as any other treatment measures for the adverse event. If an outcome for an adverse event is not available at the time of initial report, follow-up will proceed until the outcome is known.

For the purposes of this investigation, a serious adverse event will be defined as any untoward medical occurrence believed to be possibly or probably due to the study and:

1. Results in death
2. Is life threatening
3. Results in persistent or significant disability
4. Is a congenital anomaly
5. Is an important medical event that may not be immediately life threatening or results in death or hospitalization

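### The automated severe-mood alert has two different triggers: three severe ratings in one section, three consecutive severe ratings in another

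*Combined protocol and SAP*

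**What the plan says.** Mood is rated by text once a day ("Participants will respond to a daily mood rating text once a day at the end of the day") in both stages of the intervention. The stage two description under Specific Procedures keeps it: "in addition to 1 daily motivational mood rating". The schedule in Table 1 starts mood monitoring at the week 4 baseline visit, when the phone is handed over, and the last visit is at week 12.

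The response to a severe rating is described twice.

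- **iTAB-CV section**, in the paragraph on psychoeducation and device training: "Indication of severe low or high moods will trigger an automated text" directing the participant to emergency care. Then: "After 3 such texts, the system will automatically notify study staff who will follow up with the participant with a phone call".
- **Risks associated with study participation**: "There is an automated texting sequence to address texts indicating severely low or high mood", giving information on emergency services. Then: "If there are 3 such mood ratings in a row, an automatic text will be sent to the research assistant who will follow up". The contact is a telephone call here too.

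Neither section refers to the other, and no other part of the document states the trigger.

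**The concern.** Both sections describe one mechanism: a severe low or high rating, an automated message to the participant, an automated notice to staff, and a phone call. They differ in the condition for the notice. The first counts severe-mood messages and gives no time window, reset or requirement of succession. The second requires three ratings in succession. Because the alert runs automatically, one condition has to be coded.

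What is at stake is whether a participant whose severe ratings recur, but not on successive days, is phoned. The risks section itself says this population is at risk of depression and possible suicidality, and that daily ratings may detect this more readily. The staff call is the only human response that the document ties to those ratings, and visits are about four weeks apart. If the script follows one section while the risks section describes the other rule, the safeguard described is not the one in operation.

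**Working it through.** The plan gives no figure for this alert, so there is none to reproduce. The check sets the two rules side by side and then asks how far apart they can be.

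**1. Are the counted events the same?** One section counts automated messages and the other counts ratings. With one rating a day, and one message per severe rating (the natural reading), the counts are equal. The only material difference is the consecutive condition. The recipient is study staff in one section and the research assistant in the other, which is minor.

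**2. Number of ratings.** Week 4 to week 12 is 8 weeks × 7 days = 56 daily ratings.

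**3. Fixed patterns over 56 days.**

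| Pattern | Severe ratings | Three in total | Three in succession |
|---|---|---|---|
| Severe on alternate days | 28 | fires on day 5 | never fires |
| Two severe days, one not, repeated | 38 | fires on day 4 | never fires |

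The second pattern is the maximum: avoiding a run of three requires at least one non-severe day in every three, so 56 − floor(56/3) = 56 − 18 = 38. (That this equals the planned sample size is coincidence.)

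**4. How often would the rules diverge?** The documents give neither the rate of severe ratings nor their persistence, so both are assumptions. Let p be the share of days rated severe and r the probability that a severe day is followed by another. Take a stationary two-state Markov chain over 56 days with P(severe after a non-severe day) = p(1 − r)/(1 − p), and assume every text is answered. Exact probabilities of at least one alert:

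| p | r | At least 3 in total | A run of 3 |
|---|---|---|---|
| 10% | 10% (independent) | 92.8% | 4.8% |
| 10% | 50% | 79.5% | 51.6% |
| 10% | 70% | 67.8% | 59.4% |
| 10% | 80% | 58.8% | 55.8% |
| 5% | 5% (independent) | 53.5% | 0.6% |
| 5% | 50% | 44.9% | 29.8% |
| 5% | 80% | 33.3% | 32.2% |
| 2% | 2% (independent) | 10.2% | 0.04% |
| 2% | 50% | 16.7% | 13.0% |
| 2% | 70% | 16.3% | 15.5% |

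The gap is wide when severe ratings are scattered. It narrows when they persist, and its absolute size also falls when they are rare.

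**5. Unanswered texts.** Participants may leave texts unanswered, and Hypothesis 2 sets a 75% response target. The risks section does not say whether an unanswered day breaks a run. Assuming 75% of mood texts are answered, p = 10% and r = 50%, simulation of 200,000 participants gives 68.4% for three in total. For the consecutive rule it gives 36.9% if runs are counted over answered ratings and 30.7% if a missed day breaks the run. This is missing detail within one rule and is secondary to the contradiction.

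**The case against.** The strongest reply is that the passages need not conflict. The risks section says a call follows three successive severe ratings; it does not say that this is the only occasion for a call. Any run of three also makes three in total, so its case sits inside the other rule. Alternatively, the iTAB-CV section, with no window or reset, may be loose shorthand for the consecutive rule. Either is possible, but nothing in the document confirms either, and the two readings lead to different programmed triggers. A conditional that describes an automated alert is naturally read as stating when the alert fires. The script is not in the document, so what was programmed cannot be known.

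The second reply is that other contacts reduce the dependence on this call. That stands in part. The protocol provides for location checks between assessments, promises close communication to monitor for worsening, and requires the clinician and principal investigator to be notified at once if acute risk emerges during an assessment. MADRS, YMRS and BPRS are scheduled at every visit, and "Adverse events will be assessed and recorded at every visit following the Screening visit". These lower the stakes, but none is tied to the daily mood replies and none says which trigger applies.

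The third is that the probabilities rest on assumed inputs and that the independent-days figures overstate the likely gap, because moods usually carry over from day to day. That is right. The figures show only that the two wordings are not equivalent; the contradiction does not depend on them.

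**Conclusion.** The point holds. The two sections give different conditions for the same automated safety alert, and nothing in the document reconciles them. It is worth correcting but limited in consequence: the automated emergency message goes out under either wording, and neither the power calculation nor the baseline to week 12 adherence comparison is affected.

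That the rules can diverge is certain from the text, given one automated message per severe rating. How often they would diverge is not known. Under the assumed rates of 2% to 10% with every text answered, the difference in the chance of an alert runs from 88.0 percentage points (92.8% − 4.8%; 10% rate, independent days) to under 1 point (16.3% − 15.5% = 0.8; 2% rate, 70% persistence). No view is taken on which trigger is appropriate.

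**What to change.** The investigators should reconcile the two sections into one trigger of their choosing and word it identically in both. The text should say whether the count is cumulative or consecutive. If it is consecutive, it would help to add whether an unanswered day breaks the run. The texting script should then be checked against the agreed wording.

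The cost is one sentence in each of two sections and a check of the script. Sample size, visits and analysis do not change.
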